7.7 Expedited Reporting to [REDACTED]

A serious adverse event is any adverse event occurring at any dose or during any use of [REDACTED] product that:

- Results in death;
- Is life-threatening;
- Results in persistent or significant disability/incapacity;
- Results in or prolongs an existing inpatient hospitalization;
- Is a congenital anomaly/birth defect;

- Is a new cancer (that is not a condition of the study);
- Is associated with an overdose;
- Is another important medical event

All SAEs and pregnancies must be reported to the Sponsor-Investigator within 24 hours of awareness of the event. These events should be reported to [REDACTED] within 15 working days of event awareness.

The initial SAE report should be as complete as possible; however, reporting should not be delayed in order to obtain more information. Follow-ups should be reported as appropriate. The study team is required to provide follow-up information in response to queries from [REDACTED] or their designee.

All SAEs from the time the subject signs the informed consent and until 30 days after the last dose of study drug must be reported. During the period after informed consent has been obtained and before the first dose of study drug has been administered, only SAEs caused by a protocol-mandated intervention (e.g., biopsy) should be reported. Any SAE that occurs 30 days after the last dose of study drug and is assessed as possibly related to study drug must be reported.

All SAEs from the time the subject signs the informed consent and until 30 days after the last dose of study drug must be reported. During the period after informed consent has been obtained and before the first dose of study drug has been administered, only SAEs caused by a protocol-mandated intervention (e.g., biopsy) should be reported. Any SAE that occurs 30 days after the last dose of study drug and is assessed as possibly related to study drug must be reported.

All SAEs and Pregnancies/Exposure During Pregnancies should be reported via email to:
[REDACTED]

Case Type	Timeframe	Format	Method
Serious Adverse Event	15 working days of awareness	Medwatch 3500A	email to [REDACTED]
Pregnancy/Exposure During Pregnancy	15 working days of awareness	Medwatch 3500A	email to [REDACTED]

Any SAE that meets FDA reporting criteria will also be reported to [REDACTED] as per above.

7.8 Routine Adverse Event Reporting

All Grade 2 or higher Adverse Events (excluding non-clinically significant laboratory values) Adverse Events **must** be reported in routine study data submissions to the Sponsor-Investigator on the toxicity case report forms. **AEs reported through expedited processes (e.g., reported to the IRB, FDA, etc.) must also be reported in routine study data submissions.**

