2.4.5 Sacituzumab Govitecan in Metastatic Breast Cancer

In the phase 1/2 IMMU-132-01 trial, 108 patients with metastatic triple-negative breast cancer received sacituzumab govitecan as a third or higher line of therapy at 10 mg/kg on days 1 and 8 every 21 days until progression or unacceptable toxicity.³² The age range of all patients was from 31 to 80 years old with a median age of 55 years old.³² The patient population were heavily pre-treated with a median of 3 prior anticancer therapies. Some patients received up to 10 prior therapies and 69% of patients had received prior platinum agents for metastatic disease.³²

The most common adverse events were neutropenia, nausea, and diarrhea (Table 3).³² Most adverse events were managed with supportive medications or dose modifications, and the majority of patients were able to continue at the 10 mg/kg dose.³² Only three patients (2.8%) discontinued treatment due to adverse events (treatment-related grade 3 transient infusion reaction and grade 2 fatigue; non-treatment related hypertension).³² No treatment-related deaths occurred.

Table 3. Drug-related adverse events in TNBC patients			
Body system	Adverse event (AE)	All grades	Grade 3 or 4
Hematologic	Neutropenia	64%	42%
	Anemia	50%	11%
	Leukopenia	21%	12%
Gastrointestinal	Nausea	67%	6%
	Diarrhea	62%	8%
	Vomiting	49%	6%
	Constipation	34%	1%
Other	Fatigue	55%	8%
	Alopecia	36%	0%
	Decreased appetite	30%	0%
	Hyperglycemia	24%	4%
	Hypomagnesemia	21%	1%
	Hypophosphatemia	15%	9%

Out of the 108 patients, three achieved complete responses and 33 partial responses, for an objective response rate of 33% (RECIST 1.1).³² Clinical benefit rate (CR+PR+SD \geq 6 months) was 45% (49/108).³² The median time to onset of response was 2 months with a median duration of response of 7.7 months.³² Importantly, 6 patients were progression free for more than 1 year from start of treatment.³² The median PFS was 5.5 months (95% CI, 4.1 to 6.3), and the median OS was 13.0 months (95% CI, 11.2 to 13.7).³² Patients benefited from sacituzumab govitecan treatment irrespective of age, onset of metastatic disease, number of prior regimens, or presence or absence of visceral metastases.³²

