7.1.2 Expected Adverse Events for Sacituzumab Govitecan

The safety profile of sacituzumab govitecan was initially characterized based on 420 patients included in the overall safety population in the IMMU-132-01 study. These patients were treated with doses of 8 mg/kg, 10 mg/kg, 12 mg/kg, and 18 mg/kg. This population included 164 patients with breast cancer (including 108 patients with metastatic triple negative breast cancer treated with

10 mg/kg), 45 patients with urothelial cancer, 110 patients with lung cancer (small cell lung cancer and non-small cell lung cancer), and 101 patients with other epithelial cancers (including cervical, colorectal, endometrial, epithelial ovarian, esophageal, gastric, glioblastoma multiforme, head and neck, hepatocellular, prostate, pancreatic, and renal). The mean treatment duration in these patients was 160 days (7.7 cycles). The following is a summary of the safety profile; additional details can be found in the Investigator's Brochure.

Nearly all patients experienced at least one adverse event; approximately 75% of patients experienced one \geq NCI CTCAE Grade 3 AE; 41% experienced one or more SAEs. The protocol provided instructions for dose reduction and interruption, and treatment discontinuation based on toxicities. AEs led to treatment interruption in 48% of patients; however, only 11% of patients discontinued due to adverse events. Fatal adverse events (within 30 days of last dose) occurred in 6.7% of patients; however nearly all of these deaths were in the setting of disease progression.

The most frequent adverse events were gastrointestinal (nausea, vomiting, and diarrhea) and myelosuppressive (neutropenia and anemia). Nausea occurred in 67% (5% \geq Grade 3); vomiting occurred in 44% (4% \geq Grade 3), and diarrhea occurred in 62% (9% \geq Grade 3) of patients. All patients were administered prophylactic antiemetic treatments and nausea, vomiting, and diarrhea were managed according to standard treatment guidelines. With aggressive management of these toxicities, few patients required treatment discontinuation.

The most frequent myelosuppressive adverse events were neutropenia (41%, \geq Grade 3 28%) and anemia (41%, \geq Grade 3 11%). Neutrophil count decreased occurred in 18% of patients (13% \geq Grade 3) and febrile neutropenia occurred in 6%. Although treatment was interrupted due to neutropenia in 21% of patients, only one patient discontinued due to this toxicity.

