Physical exam ^b , performance status	X	X		X		X		X		X		Baseline, Day 1 all cycles, EOT
Concurrent medications (See Section 5.6)	X	X	X	X	X	X	X	X	X	X		N/A
Adverse Event assessment	X	X	X	X	X	X	X	X	X	X		All visits after baseline
Vital signs ^c	X	X	X	X	X	X	X	X	X	X		N/A
Weight ^d	X	X	X	X	X	X	X	X	X	X		Baseline, Day 1 all cycles, EOT
Height	X											Baseline
Hematology panel ^e	X	X	X	X	X	X	X	X	X	X		Baseline, Day 1 & 8 all cycles, EOT
Chemistry panel ^f	X	X	X	X	X	X	X	X	X	X		Baseline, Day 1 & 8 all cycles, EOT
TSH/fT4 ^g	X	X	X	X	X	X	X	X	X	X		Baseline, Day 1 all cycles, EOT
Coagulation panel (INR/PT/aPTT)	X											N/A
Pregnancy test ^h	X											N/A
Tumor Assessment ⁱ	X							X ⁱ		X ⁿ		Baseline, Q9 wks, EOT, F/U
Brain MRI ^j	X							X		X		Baseline, Q9 wks, EOT, F/U
Research Blood (See Section 9.3)			X						X ^k		X	N/A
Research Biopsy (See Section 9.2)		X								X		Baseline, C2/3, EOT
Research Stool Sample and Diet/Activity Questionnaires (See Section 9.5 & 9.6)			X ^l							X ^l		Baseline, C2/3, EOT

Patient Reported Outcomes (See Section 9.9)	X ^q						X ^q		X ^q			Baseline, Q9 wks, EOT Follow up (FU)
Survival Assessment (See Section 5.8)												X

- a. Medical history includes clinically significant diseases, recent infections (including administration of any antibiotics within the last 28 days), surgeries, and cancer history (including prior cancer therapies and procedures).
- b. A complete physical examination will be performed at baseline. A limited physical exam will be completed prior to therapy on Day 1 of every cycle beginning with Cycle 1.
- c. Vital signs should be collected pre-dose on dosing days and are to include measurements of heart rate, respiratory rate, systolic and diastolic blood pressure while the patient is in a seated position, and oral or tympanic temperature.
- d. Weight adjustments for sacituzumab govitecan will be done according to institutional standards. See Section 8.2.7.
- e. Hematology includes hemoglobin, hematocrit, platelet count, RBC count, WBC count, and percent and absolute differential count. Results must be available prior to the administration of study drug.
- f. Chemistry testing includes sodium, potassium, chloride, bicarbonate, glucose, BUN, creatinine, calcium, phosphorus, magnesium, total bilirubin, total protein, albumin, ALT, AST, alkaline phosphatase, and LDH. Results must be available prior to the administration of study drug.

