13 STATISTICAL CONSIDERATIONS

13.1 Study Design/Endpoints

This is a randomized phase II open label study of sacituzumab govitecan +/- pembrolizumab for patients with HR+ / HER2- MBC. Sacituzumab govitecan will be administered at a dose of 10 mg/kg IV on days 1 and 8 of each 21-day cycle, and pembrolizumab will be administered at a dose of 200 mg IV on day 1 of each 21-day cycle. The target enrollment is 110 patients; 55 per arm of treatment.

The primary endpoint is PFS defined as the time from study randomization to disease progression, per RECIST 1.1 or medical judgment, the latter based on established clinical parameters, such as rising tumor markers and physical exam evidence of progression, i.e., worsening chest wall disease, or death due to any cause, whichever occurred first. Patients alive without disease progression are censored at the date of last disease evaluation. The primary objective is to compare in the intent-to-treat (ITT) population (as defined in Section 13.5) the PFS in patients randomized to receive sacituzumab govitecan in combination with pembrolizumab (Arm A) versus those randomized to receive sacituzumab govitecan monotherapy (Arm B).

Secondary endpoints include:

- PFS according to RECIST 1.1 in the PD-L1-positive population (defined as CPS ≥ 1)
- Overall response rate (ORR) according to RECIST 1.1 in the ITT and PD-L1+ population
- Overall survival (OS) in the ITT and PD-L1+ population
- Clinical benefit rate (CBR) according to RECIST 1.1, defined as CR, PR or stable disease for ≥ 24 weeks in the ITT and PD-L1+ population
- Time to progression (TTP) in the ITT and PD-L1+ population
- Duration of response (DOR) and time to objective response (TTOR) in the ITT and PD-L1+ population
- Toxicity graded according to NCI CTCAE, Version 5.0

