13.6 Analysis of Secondary Endpoints

Efficacy Endpoints

- Among patients who initiated protocol therapy and whose tumor was centrally confirmed to be PD-L1-positive (as defined by CPS ≥ 1 using the PharmDx 22C3 assay), the efficacy, as assessed by PFS, of sacituzumab govitecan plus pembrolizumab will be compared to sacituzumab govitecan alone. PD-L1 status will be defined by central confirmation of PD-L1 testing on the baseline research biopsy, if available; if not available, then the central PD-L1 testing results from the archival sample will be used. The comparison of PFS between treatment arms in the PD-L1-positive subgroup will be exploratory.
- In the modified ITT and PD-L1-positive population, all patients who initiated protocol therapy will also be evaluated for ORR (according to RECIST 1.1), CBR, DOR, TTOR and OS.

Radiographic response will be assessed using RECIST 1.1 criteria, as defined in section 11. Objective response will require confirmatory scans or exam as indicated. The ORR (CR + PR), according to RECIST 1.1, will be reported with 95% confidence intervals. Clinical benefit is defined as CR, PR or SD ≥ 24 weeks according to RECIST 1.1 and will be reported with 95% confidence intervals. Median DOR and TTOR will be reported with ranges. Overall survival, defined as the time from randomization (or registration) to death due to any cause with censoring at date last known alive, will be reported with Kaplan Meier estimates.

For OS, the log-rank test will be one-sided. Treatment efficacy in these secondary endpoints will be assessed by Cox models adjusting for clinical factors such as age at study entry, stage (locally advanced or metastatic), visceral metastases (yes or no), level of ER expression (1-9% vs. 10% or greater), and rapid recurrence after completion of adjuvant therapy < 6 months (yes or no). Dichotomous endpoints of response will be compared using Cochran-Maentel-Haenszel chi-squared tests.

Safety and tolerability

All patients will be evaluable for toxicity from the time of their first treatment with any study agent. Toxicity will be graded according to NCI CTCAE, Version 5.0. Toxicities will be summarized by maximum grade and by treatment arm. Incidence rate of each toxicity will be reported with 95% confidence intervals. The incidence rates of any grade 3 or higher toxicity will be compared across arms using a two-sided Fisher's exact test.

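### Section 7.8 lets Grade 3+ laboratory abnormalities judged not clinically significant go unreported, and 13.6 does not commit to deriving laboratory grades from the recorded values before comparing the open-label arms

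*Combined protocol and SAP*

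**What the plan says.** Section 7.8 sends to the toxicity case report forms "All Grade 2 or higher Adverse Events (excluding non-clinically significant laboratory values"). It sets no grade above which the exclusion stops applying, does not define clinical significance, and names nobody to judge it. It has one backstop: events reported by an expedited route "must also be reported in routine study data submissions". Sections 5.5 and 7.2 add that potential drug-induced liver injury is always reported as a serious adverse event.

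Section 13.1 describes the trial: "This is a randomized phase II open label study of sacituzumab govitecan +/- pembrolizumab". On size it says: "The target enrollment is 110 patients; 55 per arm of treatment".

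Section 13.6 summarizes toxicity by maximum grade and arm, gives each toxicity's incidence with a 95% confidence interval, and states: "The incidence rates of any grade 3 or higher toxicity will be compared across arms", by a two-sided Fisher's exact test. Neither 13.6 nor 13.8.2 names the source of laboratory grades or says they will be derived from measured values.

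In the Section 10 calendar, the EDC column for both the hematology and chemistry panels reads "Baseline, Day 1 & 8 all cycles, EOT". The measured values are therefore scheduled for capture whatever is decided about adverse event status.

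**The concern.** Comparing safety between arms is a secondary objective (Section 1.3). Under 7.8 as written, whether a Grade 3 or 4 laboratory value counts as an adverse event can depend on a judgment of significance. By inference that judgment is the site's, and the site knows the arm. The protocol itself accepts that a high laboratory grade can be dismissed: the dose-limiting toxicity definition in 5.4 lets the investigator set aside certain Grade 4 hematologic toxicities as insignificant.

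Two things are at stake. If sites in both arms omit such values to the same degree, the incidence tables understate severe laboratory toxicity. If they omit them to different degrees, the between-arm comparison is biased.

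A difference is conceivable. Table 4 attaches pembrolizumab consequences to immune-related liver and renal laboratory changes, and those consequences exist only in Arm A. The same value could therefore be called significant more readily there. This is a reason to guard against asymmetry; it is not evidence that asymmetry occurred.

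**Working it through.** The plan states no expected rate, alpha or power for the Grade 3+ comparison, so there is no planned figure to reproduce. The check has two parts.

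**1. Which laboratory events are exposed?** The Grade 3-4 rates are from Table 3 (Section 2.4.5, the triple-negative cohort on sacituzumab govitecan). They are set beside the Day 8 and later Day 1 treatment criteria in 5.2.2.

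| Event | Grade 3-4 rate | Criterion in 5.2.2? | Likely to be reported? |
|---|---|---|---|
| Neutropenia | 42% | Yes (ANC; also 6.3.3) | Probably, when it blocks a dose |
| Leukopenia | 12% | No | May be omitted |
| Anemia | 11% | No; 6.3 does not mandate holds | May be omitted |
| Hypophosphatemia | 9% | No | May be omitted |
| AST/ALT elevation | not listed | Yes | Probably, when it blocks a dose |

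The exposure therefore lies mainly in the middle rows and in other chemistry values that do not gate dosing.

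**2. What could omission do?** The omission shares below are assumptions; the documents give none.

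*Equal omission.* Recorded rate = true rate × (1 − share omitted). With half omitted in both arms, leukopenia of 12% is recorded as 0.12 × 0.5 = 6%, anemia of 11% as 5.5%, and hypophosphatemia of 9% as 4.5%. No false difference arises, but each incidence is halved.

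*Unequal omission, any Grade 3+ endpoint.* Inputs:
- True rate 75% in both arms. Section 7.1.2 says of the earlier sacituzumab govitecan population: "Nearly all patients experienced at least one adverse event; approximately 75% of patients experienced one" adverse event of Grade 3 or worse.
- 55 patients per arm (13.1).
- *s* = share of Grade 3+ patients whose only Grade 3+ event is a laboratory value (assumed 10% to 40%).
- *o* = share of those omitted in one arm, none in the other (assumed 50%).
- Fisher's test at two-sided 0.05 (assumed; 13.6 gives no level), with rejection probability by full enumeration of the two binomials.

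Recorded rate in the affected arm = 0.75 × (1 − *s* × *o*).

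| *s* | Recorded rates | False difference | P(reject) |
|---|---|---|---|
| 10% | 75% vs 0.75 × 0.95 = 71.25% | 3.8 points | 4.7% |
| 20% | 75% vs 0.75 × 0.90 = 67.5% | 7.5 points | 9.9% |
| 30% | 75% vs 0.75 × 0.85 = 63.75% | 11.3 points | 19.1% |
| 40% | 75% vs 0.75 × 0.80 = 60% | 15.0 points | 32.1% |

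With no omission the rejection probability is 3.0%. With half omitted in both arms it stays near 3% for every *s* in the table.

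**The case against.** The strongest reply is that the protocol turns the most important laboratory toxicities into action events. Section 2.4.5 says "The most common adverse events were neutropenia, nausea, and diarrhea (Table 3"), and a reader might infer that the Grade 3+ comparison rests on unblinded judgment for neutropenia, the commonest severe toxicity. The documents do not support that. An ANC below the 5.2.2 and 6.3.3 threshold stops a scheduled dose, Table 6 attaches consequences to severe neutropenia, and counts are taken on dosing days. A site could hardly call such a value insignificant. The same holds for AST/ALT elevation that blocks a dose. Table 6 also acts on some other Grade 3+ toxicities when they persist or delay treatment, which narrows the gap further.

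Other parts of the reply also stand:
- It is too strong to say that any laboratory abnormality can be left out. Serious, expedited and potential liver-injury events must be recorded.
- On an any-event endpoint, an omission matters only for a patient with no other recorded Grade 3+ event.
- Both arms receive the same sacituzumab govitecan backbone, so equal omission is a reasonable default, and it leaves the size of the test intact.
- Section 13.6 names no data source. That it uses the toxicity forms alone is the natural reading, but an inference.
- Counting every derived Grade 3+ value could dilute a clinically meaningful difference. Section 5.4 itself discounts some uncomplicated laboratory grades.

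These points limit the likely size without closing the gap. Nothing in 13.6 commits to using the recorded values. The dilution point is a reason to show the derived-grade analysis beside the reported-event analysis.

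**Conclusion.** The concern holds as a gap between two sections: 7.8 has an exemption with no grade ceiling, and 13.6 has no rule for deriving laboratory grades. Outside serious, potential liver-injury and other expedited events, a Grade 3+ laboratory abnormality need not be recorded if it is judged not significant. The events chiefly exposed are leukopenia, anemia, hypophosphatemia and other chemistry values that do not gate dosing.

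Neither the size nor the direction of any effect can be determined from the documents. The 3.8 to 15.0 point range rests on an assumed laboratory-only share and on one-sided omission of half of those patients. It shows what the rule would permit and does not estimate what happened. A reader might take it to show that the Grade 3+ comparison is biased, or biased against one arm; the documents do not support either reading. The primary PFS analysis is unaffected. This is a cheap improvement to a secondary comparison.

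**What to change.** **In 13.6:**
- Derive laboratory toxicity grades by program from the hematology and chemistry values in the EDC, with the same algorithm in both arms, taking baseline into account where the grading requires it.
- Report Grade 3+ laboratory toxicity by arm from these grades.
- Present the any-Grade-3+ comparison twice: once from reported events alone, and beside it with a patient counted if either the reported or the derived grade is 3 or higher.

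Section 13.2.1 says accrual was completed at 36 months. The derivation works on values already scheduled for capture and needs no site re-entry.

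**In 7.8:** limit the exemption to Grade 2 laboratory values for any further reporting.

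**Cost:** some programming, one changed phrase, and somewhat higher Grade 3+ rates in both arms. Scheduled draws will still miss nadirs between visits, so derived grades supplement event reporting and do not replace it.

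### Section 13.6 sets no grade floor for toxicity incidence or maximum-grade summaries, but Section 7.8 requires routine entry only from Grade 2, so any-grade rates would be understated

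*Combined protocol and SAP*

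**What the plan says.** Section 7.8 (Routine Adverse Event Reporting) sets what must reach the study database. It names "All Grade 2 or higher Adverse Events (excluding non-clinically significant laboratory values") and says these must "be reported in routine study data submissions to the Sponsor-Investigator on the toxicity case report forms". It adds one exception to the grade limit: "AEs reported through expedited processes (e.g., reported to the IRB, FDA, etc.) must also be reported in routine study data submissions".

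Section 13.1 lists the safety endpoint without a grade restriction: "Toxicity graded according to NCI CTCAE, Version 5.0". Section 13.6 (Safety and tolerability) then plans three things:

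- a descriptive summary: "Toxicities will be summarized by maximum grade and by treatment arm";
- an estimate: "Incidence rate of each toxicity will be reported with 95% confidence intervals";
- one formal comparison: "The incidence rates of any grade 3 or higher toxicity will be compared across arms", using a two-sided Fisher's exact test.

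Only the third carries a grade limit. Section 13.8.2 defines the safety population as treated patients with at least one post-baseline safety assessment, and it counts the absence of adverse events as such an assessment. No other section requires Grade 1 events on the toxicity forms. The study calendar in Section 10 schedules adverse event assessments but does not change the recording rule.

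**The concern.** The analysis is worded more broadly than the data collection. A patient whose worst rash was Grade 1 is in the denominator but need not be in the numerator. An incidence reported for each toxicity, with no limit stated, will be read as the proportion of patients who had that toxicity at any grade. The collected data cannot deliver that proportion.

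Section 7.8 is also a minimum and not a prohibition. Some sites may enter Grade 1 events and others may not. In a multicenter trial, a Grade 1 row in a maximum-grade table would then partly describe site habit.

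What is at stake is the descriptive tolerability profile, which belongs to a secondary objective (Section 1.3) that names immune-related events. The effect is largest for toxicities that are mostly mild.

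**Working it through.** The plan states no figure for this point, so there is nothing to reproduce. The check is a comparison of provisions, followed by arithmetic that shows how far the documents can bound the effect.

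**Step 1: provisions side by side**

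| Element | Section | Grade limit |
|---|---|---|
| Routine entry on toxicity forms | 7.8 | Grade 2 or higher |
| Entry of expedited events | 7.8 | none |
| Incidence of each toxicity | 13.6 | none stated |
| Maximum-grade summary | 13.6 | none stated |
| Fisher comparison | 13.6 | Grade 3 or higher |
| Denominator | 13.8.2 | includes patients with no event |

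The expedited route does not close the gap. It covers serious events and, under Section 7.6.1, two events of clinical interest: an overdose without symptoms and a pattern of liver test results. Ordinary Grade 1 nausea, rash or pruritus falls outside it.

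**Step 2: formula**

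Let p be the any-grade incidence and g the share of affected patients whose worst grade is 1. If those patients are not entered, recorded incidence = p × (1 − g).

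**Step 3: what the documents can bound**

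Section 7.1.2 gives nausea as 67%, with 5% at Grade 3 or higher. The remaining 67 − 5 = 62 points are Grade 1 or 2, and the split is not given. If all are Grade 2, the recorded rate is 67%. If all are Grade 1, it is 5%. Table 3 in Section 2.4.5 gives alopecia as 36% at all grades and 0% at Grade 3 or 4, so its recorded rate could be anything from 0% to 36%. The documents go no further than this.

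**Step 4: illustration with assumed g**

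The values of g below are assumptions. The starting rates are those in Section 7.1.2.

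| Toxicity | p | g = 25% | g = 50% | g = 75% |
|---|---|---|---|---|
| Nausea | 67% | 50.3% | 33.5% | 16.8% |
| Fatigue | 53% | 39.8% | 26.5% | 13.3% |
| Alopecia | 42% | 31.5% | 21.0% | 10.5% |

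Section 13.1 gives the arm size: "The target enrollment is 110 patients; 55 per arm of treatment". For alopecia with 55 patients, 42% is about 23/55, with an exact (Clopper-Pearson) 95% interval of 28.7% to 55.9%. At g = 50% the recorded count is about 12/55, with an interval of 11.8% to 35.0%, which excludes 42%. At g = 25% it is about 17/55, with an interval of 19.1% to 44.8%, which includes 42%. The planned interval measures sampling error and makes no allowance for unrecorded Grade 1 events.

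**Step 5: what does not change**

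Grade 3 or higher events are all above the floor, so the Fisher test is unaffected. The graded dose-limiting toxicity criteria in Section 5.4 start at Grade 2, so the run-in rule in Section 13.4 is unaffected. PFS does not use these data.

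**The case against.** The best defence is that Sections 7.8 and 13.6 should be read together. Section 13.6 never says any-grade and never specifies a Grade 1 column, so the maximum grade can be taken as the maximum among recorded events. A Grade 2 collection floor is a legitimate and explicit choice, it applies equally to both arms, and the only formal safety test is untouched. All of that stands except the inference that nothing needs changing. Section 13.6 does not state the floor, and because voluntary Grade 1 entry is allowed, the tables would not be clean Grade 2 or higher tables either.

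A second defence is that mild effects are captured elsewhere. PRO-CTCAE asks about 16 symptom concepts (Section 1.4.4 and Appendix G), including nausea, rash, itching and hair loss, and TSH/fT4 is scheduled in both arms. This stands in part. PRO-CTCAE is completed at baseline, every 9 weeks and at end of treatment with a 7-day recall, and nothing in Section 13.6 feeds it into the CTCAE incidences.

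Stronger readings are tempting, and the documents do not support them:

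- A reader might infer that both arms will look better tolerated than earlier sacituzumab govitecan data. No historical toxicity comparison is planned. Table 3 also covers drug-related events in triple-negative disease, whereas Section 7.8 has no attribution limit and this trial enrolls HR+ patients.
- A reader might infer that low-grade immune events will be missing. Grade 2 events are recorded, nearly all Table 4 actions start at Grade 2 (myocarditis is an exception), and the sources just named cover some milder effects.
- A reader might put a number of percentage points on the loss. That number would rest wholly on an assumed Grade 1 share.

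**Conclusion.** The mismatch is real and limited. As written, the per-toxicity incidences and the maximum-grade summary cannot be delivered as any-grade results from the data that Section 7.8 requires. Read that way, they would be biased low, most of all for mainly mild toxicities, and any Grade 1 counts would depend on voluntary site entry. The direction follows from the text, provided that some patients have Grade 1 as their worst grade and that not all of them are entered. The size cannot be derived. The bounds and the 25% to 75% illustration show only that it could be material. If the tables are labelled as Grade 2 or higher and hold only such events, there is no understatement. The trial's formal safety test, run-in rule and primary analysis do not depend on this point.

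**What to change.** In Section 13.6, define the incidence and maximum-grade tables as Grade 2 or higher. Exclude Grade 1 events that sites entered voluntarily, or list them separately. State the floor in every table title, and do not present the figures as any-grade rates. Thyroid laboratory abnormalities of any grade may be summarized from the scheduled TSH/fT4 results in both arms.

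The cost is a few sentences in Section 13.6 and revised table titles, with no new data. Collecting Grade 1 events instead would be a burden and probably uneven at this stage, since Section 13.2.1 reports that accrual is complete. The downside of the proposed change is that the tables no longer describe all toxicities, and the report should say so.
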